The primary objective of this study is to examine the prevalence and severity of vaginal morbidity in women following treatment for localized anal cancer and to identify predictive factors, including the potential dose-response relationship between radiation exposure and morbidity. Furthermore, the study seeks to investigate possible correlations between vaginal morbidity and patient-reported sexual dysfunction.

The secondary objective is to investigate patterns of care related to managing gynecological toxicity and sexual dysfunction, including the use of dilators and hormone therapy. The study also evaluates patient satisfaction with the guidance provided to identify areas for improvement, aiming to support the development of standardized, high-quality practices that ensure consistent and patient-centered care across Denmark's three anal cancer treatment centers.

Study design

This is a national multicenter, cross-sectional study that collects quantitative and qualitative data from gynecological examinations, questionnaires, and semi-structured interviews.

Study population

Inclusion criteria:

- Female patients aged 18 or older.
- Diagnosed with AC and treated with CRT with curative intent.
- 6–36 months post-CRT.
- Willing and able to provide informed consent.

Exclusion criteria:

- History of pelvic radiotherapy for conditions other than the current diagnosis.
- Treatment with electron beam radiotherapy.
- Non-Danish speaking

Inclusion procedures

Participants will be identified during follow-up consultations (6-36 months) at Aarhus University Hospital, Vejle Hospital, and Herlev and Gentofte Hospital. When a potential participant is identified, the treating physician responsible for the consultation will provide both oral and written information about the study. Participants will be informed that they have the right to have a companion or support person present during the initial oral information consultation. To ensure sufficient time for consideration, participants will be offered an inclusion consultation at least 24 hours after the initial

consultation. During this consultation, further questions can be addressed, and participants are welcome to bring a companion or relative.

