Written informed consent will be obtained at this inclusion consultation before study participation. Patients will be assured of confidentiality. Patients will be informed that their participation is entirely voluntary and that they can withdraw their consent at any time without affecting their future care.

If they consent, the gynecological examination will either be performed shortly after consent or scheduled for their next follow-up visit, depending on patient preference and clinical feasibility.

Endpoints

Primary endpoint:

- Prevalence of vaginal stenosis grade 2 or higher.

Secondary endpoints:

- Gynecological findings: vaginal elasticity, adhesions, telangiectasias, ulceration, and bleeding.
- Radiation Dose to sexual organs at risk
- Patient-reported outcomes on sexual health issues
- Pattern of care; dilator use, lubrication, hormone treatment(local/systemic), received specialized sexual counseling.
- Patient satisfaction with the existing sexual rehabilitation program

Data collection

1. Sociodemographic data

Sociodemographic data will be collected via a case report form (CRF) during the consultation where the gynecological examination is performed. This data includes age, smoking status, menopausal status, relationship status, WHO performance status, and comorbidities. (first part of Appendix 1)

2. Clinical data

Clinical data will be extracted from medical records. They will encompass details of the anal cancer diagnosis, including tumor location (with specific information on vaginal invasion if present), tumor volume and length, histological type, and TNM classification. Information about the treatments received will be detailed, including radiation dose and fractionation schedule, as well as chemotherapy regimens. Additionally, data on any salvage surgery or recurrence will be collected, along with details of any subsequent treatments provided for the recurrence. Access to these records will be granted to the principal investigator and relevant regulatory authorities for research purposes, including monitoring, quality control, and compliance with required oversight.

3. Gynecological examinations:

Comprehensive vaginal morbidity will be assessed using an electronic case report form, as detailed in Appendix 1. The morbidity assessment form is based on vaginal morbidity documentation following radiotherapy for cervical cancer, as described by Kirchheiner (2012)¹⁶. This methodology has also been employed in Suval (2023)¹⁷.

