To ensure uniform grading of vaginal morbidity across the study sites, a dedicated seminar will be held before the initiation of patient inclusion. This seminar will involve all relevant physicians responsible for assessments at the three participating centers to align understanding and grading practices, minimize inter-observer variability, and ensure consistency in evaluations throughout the study.

4. Patient-reported outcome measures:

Electronic surveys will be sent following the control visit where the gynecological examination is performed. A reminder email will be sent after one week if a response is missing. If the patient cannot access the survey electronically, it will be handed in on paper form during the consultation and entered electronically afterward.

The survey will include validated questionnaires: the European Organization for the Research and Treatment of Cancer Quality of Life Core Questionnaire (EORTC QLQ-C30) with the Anal Cancer Module (EORTC-QLQ-ANL27), EORTC Sexual Health Questionnaire (EORTC-QLQ-SH22), and Female Sexual Function Index (FSFI). See Appendix 2 for details on these questionnaires.

In addition to the questionnaires mentioned, there will be questions regarding patterns of care, see Appendix 3

5. Radiation Dose parameter:

The principal investigator will retrospectively delineate the vagina on therapy scans from the included participants in accordance with applicable delineation guidelines. Based on this, a retrospective analysis of dose-volume histograms will be performed to identify correlations between vaginal morbidity and radiation exposure.

6. Interviews:

Semi-structured interviews with early participants will be conducted over the telephone using the interview guide provided in Appendix 4. The interviews will be conducted with notes taken on themes and quotes during the sessions for further analysis.

Data management

All data will be entered into a secure electronic database (REDCap) hosted at Aarhus University Hospital. Compliance with GDPR and Danish data protection regulations will be ensured.

Sample size and statistical analysis plan

Sample size

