Annually, approximately 120 women in Denmark undergo treatment for anal cancer, with roughly stage distributions of 25% (Stage I), 52% (Stage II), 17% (Stage III), and 6% (Stage IV)¹⁸. Using survival data from the RTOG 98-11 trial¹⁹, we calculated 1-, 2-, and 3-year survival rates assuming a linear decline from 100% survival at treatment initiation to the reported 5-year survival rates of 82% for Stage I, 74% for Stage II, 57% for Stage III, and 42% for Stage IV. From these calculations, women treated three years ago contributed approximately 99 women alive, those treated two years ago contributed 106, and those treated one year ago contributed 113, yielding a total of 318 women who have received treatment for anal cancer within a period of three years are alive and eligible for follow-up. Given the sensitive nature of topics such as gynecological toxicity and sexual dysfunction,

we conservatively estimate a participation rate of 30%. This results in an expected inclusion of 80 participants.

This sample size of approximately 80 participants will allow us to achieve 80% statistical power to detect a correlation between radiation dose and vaginal stenosis, with a significance level of 0.05 and an assumed moderate correlation coefficient of $r=0.3$. This power calculation ensures that the study is adequately designed to investigate the potential dose-response relationship.

For the semi-structured interview sub-study, 20 participants are initially included to explore patient satisfaction with the sexual rehabilitation program. Thematic analysis will guide data collection and analysis, following an iterative approach to identify saturation. Saturation is defined as the point where no new themes, patterns, or insights emerge, ensuring data utility is maximized.

If thematic saturation is not reached after the initial sample, additional participants will be included in batches of 5 participants. This approach ensures robust, comprehensive findings aligned with the research objectives while maintaining methodological rigor.²⁰

Statistical analysis plan

Vaginal stenosis grade 2 or above, will be calculated as the proportion of participants meeting the criteria out of the total number of participants. A 90% confidence interval (CI) will be used to indicate the uncertainty surrounding the prevalence estimate.

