Physician-reported vaginal outcomes: Variables such as adhesions, elasticity, telangiectasias, ulcerations, and bleeding will be summarized using descriptive statistics

Patient-reported outcomes (PROs): Data from the Female Sexual Function Index (FSFI), EORTC-QLQ-SH22 and EORTC-QLQ-C30 with the ANL24 supplement will be analyzed. Scores will be calculated according to the respective guidelines, transforming raw data into standardized scores. Comparisons across groups (e.g., stenosis vs. no stenosis) will be made using appropriate tests such as t-tests or Mann-Whitney U tests.

Dose-response relationship: This will be explored using logistic regression, assessing the relationship between radiation dose and vaginal stenosis grade 2 or above. A dose-response curve will also be generated using spline regression to visualize potential non-linear relationships.

Patient care satisfaction: Data from semi-structured interviews will be analyzed using thematic analysis to identify key themes and patterns related to patient satisfaction with guidance and counseling on gynecological and sexual issues post-treatment. Notes will be coded in an exploratory manner, allowing themes to emerge from the data and ensuring a comprehensive understanding of patient experiences and perspectives.

All analyses will be conducted using a predefined statistical significance level of 0.05. Results will be reported with appropriate measures of uncertainty, such as confidence intervals. Quantitative data analyses will be performed using StataSE18 software, and qualitative data will be analyzed using NVivo14 software.

Study schedule (tentative)

Protocol approved: Awaiting

Inclusion start: 01.05.2025

Inclusion end: 01.05.2026 2026

End of data collection: June 2026

Data analysis and interpretation: Fall 2026

Plans for dissemination and reporting

The findings of this study will be disseminated to ensure academic and public access to the results. Planned activities include publishing study results in peer-reviewed scientific journals and presentations at national and international conferences focusing on oncology, radiation therapy, and survivorship care. All results, whether positive, negative, or inconclusive, will be published to contribute to the broader evidence base.

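### Satisfaction with sexual rehabilitation, a secondary endpoint serving a three-centre aim, rests on about 20 interviews chosen by early enrolment, which does not secure adequate coverage of each centre

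*Protocol*

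**What the plan says.** The Endpoints section of the protocol lists, among the secondary endpoints, "Patient satisfaction with the existing sexual rehabilitation program". The Purpose section gives the reason for measuring it: to find areas for improvement and so help to "ensure consistent and patient-centered care across Denmark's three anal cancer treatment centers".

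Three sections fix how it is measured.

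- **Data collection, 6. Interviews:** "Semi-structured interviews with early participants will be conducted over the telephone", with the guide in Appendix 4.
- **Sample size:** "20 participants are initially included to explore patient satisfaction with the sexual rehabilitation program". If saturation is not reached, "additional participants will be included in batches of 5 participants". Saturation is defined by the absence of new themes; centre plays no part in the definition.
- **Statistical analysis plan, patient care satisfaction:** "Data from semi-structured interviews will be analyzed using thematic analysis to identify key themes and patterns related to patient satisfaction". No other source for this endpoint is named.

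None of these sections states a minimum per centre or any criterion for choosing interviewees other than early participation. The pattern-of-care questionnaire in Appendix 3, which belongs to the survey for all participants, asks about dilation, hormone therapy and consultations with a sexual health nurse or sexologist. It does not ask how satisfied the woman was with the guidance she received.

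**The concern.** A qualitative sample need not be statistically representative, but it should cover the variation that the question is about. Here the question concerns guidance as delivered at three centres, and the Background says that the type and extent of counselling are not systematically documented. When practice is undocumented, the safe course is to hear from every centre. Selection by early enrolment leaves this to chance, and a saturation rule based on themes can be met while one centre has hardly been heard.

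At stake is whether the themes can be taken to describe guidance at all three centres. There is also no second source to fall back on. The women who are not interviewed are never asked to rate their satisfaction, and a question that was not asked cannot be recovered at analysis.

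**Working it through.** **Is there another source for the endpoint?** The instruments in Appendices 2 and 3 were compared with the endpoint.

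- FSFI and QLQ-SH22 each have a satisfaction scale, but it concerns sexual satisfaction, not the program.
- QLQ-SH22 also covers communication with professionals. This is related, but it does not rate the rehabilitation program.
- Appendix 3 has an answer option for women who had no consultation but wanted one, and open questions on why dilation was not done or was stopped. These show unmet need, not satisfaction.

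The interviews are therefore the only source. With 20 interviews among 80 expected participants, 80 - 20 = 60 women give no satisfaction information unless further batches are drawn.

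**How likely is poor coverage of a centre?** The 20 interviews are a starting number governed by saturation, so the plan has no formula to reproduce.

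Inputs from the protocol: N = 80 expected participants, n = 20 initial interviews, 3 centres. Assumed, because the protocol gives no centre shares: a smallest centre with K of the 80 women. Also assumed: early enrolment acts like a random draw with respect to centre.

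Drawing without replacement, P(X = x) = C(K, x) × C(80 - K, 20 - x) / C(80, 20).

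For K = 12 (15%):
- P(0) = 0.023
- P(at most 2) = 0.0232 + 0.1138 + 0.2378 = 0.375

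For K = 16 (20%):
- P(0) = 0.006
- P(at most 2) = 0.0055 + 0.0395 + 0.1223 = 0.167

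A binomial model, P(X = x) = C(20, x) p^x (1 - p)^(20 - x), ignores the finite total and serves as a check. For zero interviews it gives 0.85^20 = 0.039 and 0.80^20 = 0.012.

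| Share of smallest centre | Expected interviews | No interview: draw from 80 | No interview: binomial | At most 2: draw from 80 | At most 2: binomial |
|---|---|---|---|---|---|
| 10% (8 of 80) | 2 | 8.8% | 12.2% | 68% | 68% |
| 15% (12 of 80) | 3 | 2.3% | 3.9% | 37.5% | 40.5% |
| 20% (16 of 80) | 4 | 0.6% | 1.2% | 16.7% | 20.6% |
| 25% (20 of 80) | 5 | 0.1% | 0.3% | 6.2% | 9.1% |

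With nearly equal centres (27, 27 and 26 women), the chance that any centre is missed is 0.02%, and the chance that the centre with 26 gives two or fewer interviews is 1%.

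**Do the extra batches cure it?** Only in part. By the same formula for the 20% centre (16 of 80), the chance of two or fewer interviews falls from 16.7% with 20 interviews to 6.1% with 25 and 1.8% with 30. But batches are triggered by new themes, not by a poorly covered centre, so nothing in the rule ensures that they are drawn when needed.

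**The case against.** The strongest reply is that this is an exploratory qualitative sub-study. It promises no figure per centre, and its guide in Appendix 4 asks about timing, amount of information, preparedness, barriers and suggestions, so it can identify areas for improvement whatever the centre mix. Twenty is a starting number that can grow. The wording about early participants does not say the first 20 in strict order, and it does not forbid spreading them over centres. The survey also captures some unmet need from everyone. All of this is fair, and it is why the point is minor. It does not answer the narrower observation that the plan states a selection rule and a stopping rule, and neither secures coverage of the three centres named in the aim.

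A reader might infer more than the protocol supports:

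- **That a centre will probably be missed altogether.** At a 15-20% share the chance is only about 1-2% (1-4% under the binomial model). It becomes material only for a much smaller centre.
- **That a centre opening late would be left out.** At even accrual over the 12-month inclusion period, the first 20 of 80 would enter in 12 × 20/80 = 3 months. However, the protocol gives a single inclusion start date and a seminar for assessors from all centres beforehand. Nothing points to staggered opening.
- **That comparing centres is an objective.** The Purpose section speaks of consistent care; no comparison of centres is planned.
- **That counselling is known to differ by centre.** The protocol says only that documentation is lacking.
- **That early participants are the most willing women.** Women are identified at follow-up consultations, so entry depends at least partly on appointment dates.
- **That telephone interviewing is a weakness.** Nothing in the protocol shows harm from it.

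**Conclusion.** The point holds as a modest design weakness. A listed secondary endpoint that serves a three-centre aim has one source, about 20 interviews with women who enrol early, with no safeguard for centre coverage and no rating from the other roughly 60 women. The likely harm is thin coverage: two or fewer interviews from a centre with a 15-20% share in about 17-38% of cases (21-40% binomial).

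These figures rest on assumed centre shares and on treating early enrolment as random with respect to centre. With nearly equal centres the risk is negligible; with a 10% centre it is more likely than not. The primary endpoint and the dose-response analysis are unaffected. The matter belongs in the protocol because the selection rule and the questionnaire are both fixed there.

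**What to change.** 1. In Data collection, 6. Interviews, replace selection of early participants with selection across all three centres and a stated minimum per centre. Five each would commit 3 × 5 = 15 of the initial 20 and leave 5 free. State what happens if a centre enrols too few women, for example that every willing participant there is invited.
2. In Sample size, allow saturation to be declared only once all three centres are represented at that minimum.
3. Add one item to Appendix 3 on satisfaction with the guidance and counselling received, for example on a four-point scale. Report it descriptively, overall and by centre, with no test between centres. This raises the base for a satisfaction rating from none to up to 80 answers.
4. Name the new item next to the interviews as a source for this endpoint in the Statistical analysis plan.

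The cost is an interview window that may run over more of the inclusion year, and one extra survey question. If inclusion has already begun, women who have already completed the survey would lack the item unless it is sent to them separately, and the number of answers should be reported accordingly.

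### The expected inclusion of 80 does not follow from 318 women at 30% participation (95); the step between them, plausibly the 6–36 month window, is not stated

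*Protocol*

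**What the plan says.** The Sample size section of the Protocol starts from "Annually, approximately 120 women in Denmark undergo treatment for anal cancer", with stage shares of "25% (Stage I), 52% (Stage II), 17% (Stage III), and 6% (Stage IV"). It assumes a straight-line fall in survival to quoted 5-year rates of 82%, 74%, 57% and 42% for stages I to IV. It reports 113, 106 and 99 survivors among women treated one, two and three years ago, and gives the total as "318 women who have received treatment for anal cancer within a period of three years are alive and eligible for follow-up".

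One factor follows: "we conservatively estimate a participation rate of 30%. This results in an expected inclusion of 80 participants". The next paragraph carries the number forward: "This sample size of approximately 80 participants will allow us to achieve 80% statistical power", for a correlation of 0.3 at a significance level of 0.05. Sidedness is not given.

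The Study population section sets narrower limits than the pool. Women must be "6–36 months post-CRT" and "Diagnosed with AC and treated with CRT with curative intent". The exclusions include "History of pelvic radiotherapy for conditions other than the current diagnosis", electron beam treatment and not speaking Danish. The Sample size section mentions none of these as a reduction and puts no number on any of them.

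**The concern.** The text names a pool and a rate and presents 80 as their product, but the product is 95. The gap of 15 women is 19% of the stated figure, too large for rounding or for the approximate nature of the inputs. This is the only derivation of the sample size in the Protocol, and the power sentence takes its number from it. A reader cannot tell whether the multiplication is wrong, the participation rate is really lower, or a restriction of the pool was applied and left out. The answer settles how many women the three centres expect to approach, and what share of them must agree.

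**Working it through.** **Inputs (Protocol, Sample size).** 120 women a year; stage shares 0.25, 0.52, 0.17, 0.06; 5-year survival 0.82, 0.74, 0.57, 0.42 with linear decline; participation 0.30. From Study population: window of 6–36 months.

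**1. Reproduce the pool.**
- Average loss per year = (0.25 × 0.18 + 0.52 × 0.26 + 0.17 × 0.43 + 0.06 × 0.58) / 5 = 0.2881 / 5 = 0.05762.
- Alive after t years = 120 × (1 − 0.05762 t): 113.1 at t = 1, 106.2 at t = 2, 99.3 at t = 3.
- Sum = 318.5, against 318 stated. The pool reproduces.

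**2. Apply the stated rate.**
- 0.30 × 318 = 95.4, against 80 stated. This step does not reproduce.

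**3. What 80 would need.**
- At 30%: 80 / 0.30 = 266.7 women, which is 51 fewer than 318 (a 16% cut).
- On 318 women: 80 / 318 = 25.2% participation.

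**4. Restrictions that the Protocol's own figures can size.**

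| Unstated step | Pool | × 0.30 |
|---|---|---|
| None | 318 | 95.4 |
| Remove all stage IV, an extreme reading of curative intent: 318.5 − 120 × 0.06 × [3 − (0.58/5) × 6] = 318.5 − 16.6 | 301.9 | 90.6 |
| 6–36 months, as 30 of 36 months: 318 × 30/36 | 265 | 79.5 |
| 6–36 months, linear survival integrated from 0.5 to 3 years: 120 × [2.5 − 0.05762 × (9 − 0.25)/2] | 269.7 | 80.9 |
| 6–36 months, by halving the first-year group: 318 − 56.5 | 261.5 | 78.5 |

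Stage IV alone does not reach 80. The time window does, to within rounding, under each way of applying it. The exclusions for other pelvic radiotherapy, electron beam treatment and language cannot be sized from the document.

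**5. The power sentence at the number it uses.** Fisher's z, r = 0.3, atanh(0.3) = 0.3095.
- Power = Φ(0.3095 × √(N − 3) − z), with z = 1.960 two-sided or 1.645 one-sided at 0.05.
- N = 80: 0.3095 × √77 = 2.716. Two-sided Φ(0.756) = 77.5%; one-sided Φ(1.071) = 85.8%.
- N for 80% power, two-sided: [(1.960 + 0.842) / 0.3095]² + 3 = 84.9, so 85 women.
- For comparison, N = 95: 84.3% two-sided, 90.7% one-sided.

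**The case against.** The strongest reply is that nothing was multiplied wrongly and a line was simply left out. The 318 are described as treated within three years and eligible for follow-up, which can mean women in clinical follow-up from month 0 to 36 rather than women who meet the study criteria. The inclusion criteria and the Inclusion procedures section both restrict recruitment to 6–36 months, and that restriction takes 30% of the pool to about 80.

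Much of this stands. A reader might infer that the right number is simply 95. The documents do not support that, because a count that includes women less than six months after treatment would conflict with the inclusion criteria. A reader might also infer that the Protocol offers no clue to the origin of 80, or that only the stage IV share can be sized. That is too strong as well, since the window can be sized from the stated inputs.

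What does not stand is that the text is therefore sound. The Sample size section never applies the window and presents 80 as the direct result of 30% participation. It also builds the pool from women treated one, two and three years ago, and a woman treated a year ago is already past six months, so the cut does not follow from the pool as described. A participation rate of about 25% on all 318 gives the same 80 (0.25 × 318 = 79.5), so the window is plausible but not shown.

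A second reply is that the power sentence gives its own sample size, correlation and significance level, so it can be checked however 80 arose. That is correct.

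**Conclusion.** The concern holds as a gap in the derivation. The stated inputs give 95 and the Protocol states 80, with the step between them missing. Restriction to 6–36 months, leaving about 265–270 women, is a plausible explanation but an inference; a lower participation rate is equally compatible with the number.

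The consequence is limited. Against the stated inputs, 80 is the cautious figure for recruitment, and no endpoint or study procedure depends on the correction. The inputs are themselves approximate: linear survival, rounded stage shares and an assumed participation rate.

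A reader might infer that the faulty derivation causes a power shortfall. It does not. At 80 women, power for r = 0.3 is about 77.5% if the test is two-sided, slightly under the claimed 80%, and about 86% if one-sided, wherever the 80 came from. Both figures assume a Fisher z test of a correlation. The power sentence belongs in the same correction because it uses this number and leaves sidedness open.

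**What to change.** In the Sample size section:

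1. State and quantify the step from 318 to 80. If the time window was meant, write that about 265–270 of these women are expected to be within 6–36 months of chemoradiotherapy and that 30% of them is about 80. If a lower participation rate was meant, give that rate (about 25% of 318).
2. Keep 318 as the starting count of survivors if wanted, but do not describe it as the pool to which 30% is applied. Use about 95 only if no restriction was intended and the 318 do meet the inclusion criteria.
3. Make the power sentence match the resulting number and state sidedness. With 80 women and r = 0.3, it should read about 77.5% for a two-sided 0.05 test (85 women for 80%) or about 86% one-sided.

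The cost is a rewording of two adjoining paragraphs, with no change to recruitment, procedures or endpoints.
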